8.4 Early termination due to lost to follow up or other reason

Sites should make and document reasonable efforts to contact and schedule study visits. Participants who will not or cannot return for follow-up visits as planned in the protocol will be considered as non-compliant with the study protocol. This group includes:

- Patients who are uncooperative and/or refuse to return for follow-up for three consecutive visits
- Patients who relocate without notifying the investigator and cannot be located for continued follow-up arrangements.

These patients are considered "lost to follow up".

Other reasons for early termination:

- Revision of the Study device Patients who would need a revision surgery after the primary
 dual mobility surgery will automatically be withdrawn from the study follow up as the study
 device/s will no longer be in situ. This study participant will be marked as "End of Study".
 However, any study data collected up to the revision surgery and reason for revision will be
 included in the data analysis. Data related to revisions and hip-/ procedure-/ device- related
 adverse events will be assessed as secondary objectives for this study.
- Death of a study Patient Any patient who is deceased while on the study should be marked as End of Study and thus withdrawn.

Patients who are considered "lost to follow up" or have early terminated the study must have documentation indicating the date, the reason (if available) and the last date of follow-up available.

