This visit will occur 0-6 days from the date of surgery while the patient is still at the hospital. Standard of care assessments will be performed which include X-rays of the treated hip. Postoperative pain management will be under the decision of the orthopaedic surgeon and support staff who will provide instructions to the patients regarding home care during the first few weeks after surgery. Medications are often prescribed for short-term pain relief after surgery. The rehabilitation program will depend on patient's goals and desired activities according to the SOC at the site. The goal of physical therapy intervention during the early post-operative phase is to decrease swelling, increase range of motion, enhance muscle control and strength in the involved lower extremity and maximize patients' mobility with a goal of functional independence.

Rehabilitation program may be individualized in function of bone quality, age, health and physical fitness of the patient. Any substantial changes to the SOC rehabilitation program will be documented. Immediate post-op complications/AEs related to the hip, or the surgery will be recorded. Any Serious Adverse Event (SAE) related to the treated hip and/or device-related incident will be recorded and reported to the Sponsor as per guidelines.

Follow Up Visits 4, 5, 6, 8, 9 and 11

The follow-up visits will be performed per the Schedule of Events table (Table 1). The study participants will be encouraged to attend site visits up to Visit 6 within the scheduled visit window to complete study assessments and questionnaires. X-rays of the treated hip will be completed as

per the schedule. When participants are unable to visit the study sites physically, participants will be encouraged to complete study questionnaires at home and provide any relevant complications/ Adverse Events information via email. When a study patient is unable to visit the study site as per the schedule of events, a protocol deviation will be reported with justification and a description of the corrective action plan to prevent a future occurrence.

Telephone Interview – Visit 7 and 10

At this contact, a designated delegated team member will telephone the participant to enquire about any complications. Any Adverse or Serious Adverse Event (SAE) or device-related incident will be recorded and reported to Corin as per guidelines. The participant will be reminded about the 10-year FU visit.

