8.3 Postoperative Withdrawal

After the surgery, the participant may voluntarily revoke consent and withdraw from the study at any time without reason. Participants may be involuntarily exited from the study for failure to comply with the study protocol, failure to attend follow-up visits or for any clinical condition, if the Investigator deems it necessary.

In all cases, the Investigator should record the withdrawal indicating the date, the reason (if available) and the last date of follow-up available. All data obtained up to consent withdrawal will be included in the analysis.

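### Sections 8.3 and 8.4 allow patients who report from home under 7.7 to be exited for non-attendance, so obtainable OHS and revision data can be lost, possibly selectively

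*Protocol*

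**What the plan says.** Three places in the protocol deal with a patient who does not come to a visit.

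- **Section 7.7** (follow-up Visits 4, 5, 6, 8, 9 and 11): "When participants are unable to visit the study sites physically, participants will be encouraged to complete study questionnaires at home", with complications and adverse events sent by email. The missed attendance is handled as a deviation: "a protocol deviation will be reported with justification and a description of the corrective action plan to prevent a future occurrence". Visits 7 and 10 (4 and 9 years) are telephone contacts about complications.
- **Section 8.4**: "Participants who will not or cannot return for follow-up visits as planned in the protocol will be considered as non-compliant with the study protocol". Two examples follow, introduced as included in the group and so not exhaustive. One is "Patients who are uncooperative and/or refuse to return for follow-up for three consecutive visits"; the other is patients who move away unannounced and cannot be traced. The group is then labelled lost to follow-up, under a heading on early termination. The section also asks sites for reasonable, documented efforts at contact.
- **Section 8.3**: "Participants may be involuntarily exited from the study for failure to comply with the study protocol, failure to attend follow-up visits". A clinical condition is a further ground, and the exit is subject to the investigator's judgement. On data handling it says only: "All data obtained up to consent withdrawal will be included in the analysis".

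No section says which of these prevails, and none provides for OHS or revision follow-up after an exit for non-attendance.

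**The concern.** The data most exposed do not require attendance. The primary endpoint (section 4.1) is the change in a patient-completed score, which section 9.1 allows on paper or electronically. Revision and adverse event status can be obtained by telephone or email, as section 7.7 already provides. In the section 7.6 schedule, the Harris Hip Score and X-rays are optional at 1, 5, 7 and 10 years, so the non-optional assessments at those visits are questionnaires and adverse events.

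An exit for non-attendance would therefore discard information the patient was still willing to give. The reasons for not attending (disability, a poor hip, dissatisfaction, distance) may be related to outcome. If so, the 2-year OHS mean would describe attenders only, the crude revision rate would miss later revisions, and censoring in the Kaplan-Meier analysis could be informative. An analysis plan cannot recover data that were never collected, so this belongs in the protocol.

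**Working it through.** **1. One patient under the three sections.** Take a patient who cannot travel but returns the OHS from home.

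- Under 7.7: data collected, deviation logged, patient stays in the study.
- Under 8.4: within the non-compliant group, because inability to return is joined with unwillingness. The patient fits neither listed example, but the list is not exhaustive.
- Under 8.3: may be exited on either of two grounds, non-compliance or non-attendance, after any number of missed visits.

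The non-compliant label alone does not conflict with 7.7, which also treats the missed visit as a departure from protocol. The conflict lies in the exit and in the lost-to-follow-up status.

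**2. When each rule can act.** Visit 3 takes place in hospital, so the first three visits a patient can refuse to return for are Visits 4, 5 and 6 (3 months, 1 year, 2 years). The three-visit rule is met only once the 2-year visit itself has been refused, when the 2-year OHS has already been due and the home route was available. Before 2 years the exposure comes mainly from the unrestricted 8.3 exit. After Visit 6, consecutive site visits are 8, 9 and 11, with telephone Visits 7 and 10 between them. The text does not say whether answering the telephone breaks a run of three. Both sections can act in this period.

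**3. The plan's own figure.** Section 10.2 gives n = 100 hips, mean change 22.6, SD 9.8 (taken as the SD of the change), two-sided alpha 0.05 and power above 0.90. For a paired t-test the noncentrality is 22.6/9.8 × √100 = 23.06, and power is about 1.00. The stated figure is reproduced. Five pairs already give 0.964, and power is still about 1.00 at 50 hips. Loss of hips therefore threatens bias, not power.

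**4. Possible bias in the OHS mean.** The protocol gives no dropout rate and no outcome difference, so both are assumed. With f the share lost and D the shortfall in their mean change, the attender-only mean is overstated by f × D:

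- f = 0.10, D = 5: 0.5 points
- f = 0.20, D = 8: 1.6 points
- wider range, f = 0.30, D = 15: 4.5 points

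For scale, the 95% CI half-width is t × SD/√n = 1.984 × 9.8/10 = 1.9 points at n = 100, and 2.2 at n = 80. If non-attenders did better than attenders, D would be negative and the mean understated.

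**5. Possible effect on the revision rate (illustration).** Assume a true cumulative rate of 5%, 20% of hips exited before any event, exited hips at k times the risk of retained hips, and no events seen after exit. The rate among retained hips is r = 0.05/(0.2k + 0.8), and the crude rate over all 100 hips is 0.8r:

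- k = 1: r = 5.0%, crude 4.0%
- k = 2: r = 4.2%, crude 3.3%
- k = 3: r = 3.6%, crude 2.9%

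With all hips in the denominator, the crude rate falls even without selection (k = 1).

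**The case against.** A reader might infer that these data will be lost, and lost selectively. The text does not fix that. Exit under 8.3 is permitted, not required, and depends on the investigator's judgement. Section 8.4 first asks for efforts at contact. Its listed groups are refusers and untraceable patients, not people answering from home. Data obtained before withdrawal are kept. That selectivity would occur, and in which direction, cannot be shown from the protocol.

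A reader might also infer that three refused visits end follow-up just as the primary OHS falls due. They do not, as step 2 of the working shows. After 2 years, if visits are counted as numbered, every run of three includes a telephone visit, so a patient who answers the phone would break the run.

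The size is also assumed throughout and supposes that every such hip is in fact exited. Even 1.6 points is about 7% of the assumed 22.6-point change (1.6/22.6) and is smaller than the CI half-width.

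These limits stand. What remains is that 8.3 has no threshold and no exemption for patients using the route 7.7 gives them, and 8.4 treats being unable to return like being unwilling. In a multi-centre study that leaves each site to decide, so identical patients may be kept at one site and exited at another.

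**Conclusion.** The point holds as a possibility created by unreconciled wording: obtainable OHS and revision data can be lost, possibly selectively. Before 2 years this comes mainly through the discretionary 8.3 exit; afterwards it can come through both 8.3 and 8.4. Under the assumed 10% to 20% loss and 5 to 8 point shortfall, the OHS mean would be overstated by 0.5 to 1.6 points. That would not change a conclusion that OHS improves, and power is unaffected. The 10-year revision and survival endpoints may be the more sensitive, since events are few and follow-up is long, but the figures for them are likewise illustrative. The change is worth making because the loss is avoidable and cannot be repaired at analysis.

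**What to change.** Reconcile 8.3 and 8.4 with 7.7:

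- (a) In 8.3, delete non-attendance at follow-up visits as a ground for involuntary exit. State in 8.3 and 8.4 that a patient who supplies data remotely is neither exited nor classed as lost to follow-up for not attending.
- (b) In 8.4, count a scheduled contact as missed only when neither the questionnaire nor adverse event/revision status was obtained by any route (clinic, home, email or telephone). Apply the three-consecutive rule only to such contacts.

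Leave the separate rules for revision, death and withdrawal of consent as they are; this point gives no reason to change them. The cost is a wording amendment and a few more phone or email contacts, using routes the protocol already provides. A missed site visit can still be logged as a deviation under 7.7.

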6.0 STUDY POPULATION

Participants will be selected for recruitment into the study from the general population of patients requiring a primary total hip arthroplasty surgery with a dual mobility construct and considered suitable for the cementless MobiliT cup with ECiMa insert with Paragon or TaperFit stem. Participants who do not meet the inclusion criteria or meet any exclusion criteria are excluded from the study participation. Bilateral participants will be included, and each hip will be assigned a specific study ID and the patient will complete separate questionnaires for each treated hip.

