7.4 Survivorship Analysis

Survival analysis of the study devices is calculated with the use of Kaplan-Meier estimation and 95% confidence interval. The analysis will be performed with the following end points:

- Revision of the acetabular component due to dislocation
- Revision of the femoral and/or acetabular component due to failure of the stem (such as stem fracture)
- Revision of the femoral and/or acetabular component due to aseptic loosening
- Definite or probable radiographic evidence of loosening of the components (such as lysis).

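### Section 8.4 ends the study for any revised participant because no study device remains, which is untrue after partial revisions and unclear for a bilateral patient's other hip, so follow-up data are lost.

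*Protocol*

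**What the plan says.** Section 8.4 lists revision among the reasons for early termination. For a patient who needs one, the operative words are "dual mobility surgery will automatically be withdrawn from the study follow up as the study". The reason given, and the marking that results, are worded for the person: "device/s will no longer be in situ. This study participant will be marked as 'End of Study". The rule makes no distinction by component revised or by hip.

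The same paragraph limits the consequence by keeping earlier data in the analysis: "However, any study data collected up to the revision surgery and reason for revision will be". It also assigns revisions and related adverse events to the secondary objectives, in a sentence that opens "Data related to revisions and hip-/ procedure-/ device- related".

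Other sections bear on the rule:

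- Section 6.0: "Bilateral participants will be included, and each hip will be assigned a specific study ID", with separate questionnaires for each hip. Section 6.2 requires consent for each joint, and Section 10.2 sets the sample size in hips.
- Section 7.4 defines Kaplan-Meier endpoints by component and cause. One concerns the acetabular component alone (dislocation). Another is "Revision of the femoral and/or acetabular component due to aseptic loosening".
- Section 10.1 lists, for each revision, the components revised.
- Section 4.1 makes OHS improvement to 2 years the primary endpoint. Section 4.2 asks for revision rate, survival and adverse events to 10 years.

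**The concern.** The study construct is a cup, an insert and a stem. If a revision exchanges only some of these, a study component stays in the patient, but the protocol stops watching it because it presumes that nothing is left to watch. In a bilateral patient the same rule, read literally, also closes a hip that has not been revised.

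Two things are at stake. First, a hip revised before 2 years has no 2-year OHS, so the primary result describes only hips unrevised at that point. Second, the 10-year safety and survival aims lose later events on retained components, re-revisions, and possibly the second hip. These are limits on data collection. A statistical analysis plan can choose how to treat missing values, but it cannot recover observations that the protocol tells sites not to make.

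**Working it through.** **Step 1. Does the premise hold within the protocol?**

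| Case | Study component still in situ? | Under Section 8.4 |
|---|---|---|
| Cup, insert and stem all exchanged | No | Ended; premise true |
| Stem-only revision | Yes, cup | Ended; premise false |
| Cup-only revision | Yes, stem | Ended; premise false |
| Other, unrevised study hip of a bilateral patient | Yes, all | Ended if participant means person; not if it means hip ID |

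The and/or wording in Section 7.4 and the listing of components revised in Section 10.1 show that the middle two rows are expected.

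**Step 2. Which survival information is lost?** A first revision that meets a Section 7.4 endpoint is an event for that endpoint, and it counts in the crude revision rate. The loss comes afterwards. If a stem is revised for stem failure and the cup is retained, the stem endpoint has its event, but a later cup revision for dislocation is never seen. If the first revision is for a cause outside the Section 7.4 list, such as infection, follow-up for all four endpoints stops.

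**Step 3. The plan's own sample-size figure.** Inputs from Section 10.2: mean change 22.6, SD 9.8 (taken as the SD of the paired difference), n = 100, two-sided alpha 0.05. The noncentrality is 22.6/9.8 × √100 = 23.1, and power from the noncentral t distribution exceeds 0.999. The stated power above 0.90 is reproduced. Five pairs already give 0.964, so losing a few hips does not threaten it. The 95% confidence interval half-width is 1.96 × 9.8/√100 = 1.92 points.

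**Step 4. Size of the effect on the primary mean.** Let p be the fraction of hips revised before 2 years and s their shortfall in OHS gain. If unrevised hips gain m on average, all hips gain (1 − p)m + p(m − s) = m − ps. Leaving revised hips out therefore overstates the mean by p × s.

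Section 3.1 gives these figures for p, all from other cohorts:

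- 98.7% implant survival at a minimum of 2 years, so 1.3% failed.
- 97.03% cup survival at 12 months and 96.7% predicted at 5 years, so 3.0% and 3.3%.
- In the sponsor's ongoing study with the standard insert, 16 of 1100 revised (1.5%, varying follow-up) and 95.89% survival at 5 years, so 4.1%.

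I take 1.3 to 3.3% as the range at 2 years. The documents give no value for s; I assume 10 to 20 points.

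- Low: 0.013 × 10 = 0.13 points.
- High: 0.033 × 20 = 0.66 points.
- With the 5-year figure of 4.1% as an outer check: 0.041 × 20 = 0.82 points.

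All lie inside the 1.92-point half-width and are small beside a 22.6-point expected gain.

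**The case against.** The strongest reply is that ending device follow-up at revision is normal and the protocol does not hide failures. Much of this stands. A reader might infer from the word withdrawn that failures drop out of the survival data. They do not: Section 8.4 keeps the revision, its reason and everything before it, and Section 10.1 reports crude revision rates with reason, time and components. For a fully revised hip, stopping device survival at that point is correct.

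A reader might also infer that the bias always favours the device. That is not shown. The OHS shift is favourable only if revised hips do worse, which is plausible but assumed. Losing a well-functioning second hip does not raise the mean, and hips revised after 2 years have already had their primary assessment due.

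Loss of the second hip is itself a reading. Given the hip-level IDs and consent, participant in Section 8.4 could mean the hip ID. The text does not say, so sites may apply it differently.

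Section 8.3 might be drawn in as a further source of loss: "Participants may be involuntarily exited from the study for failure to comply with the study protocol, failure to attend follow-up visits". But that exit is permissive and left to the investigator's judgement, and Section 7.7 encourages home questionnaires for those who cannot attend. It does not support a request to delete the provision.

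Finally, an OHS obtained after revision partly reflects a replacement implant, so a result restricted to hips with the device in situ is a legitimate target. That argues for reporting both results. It does not argue against collecting the data.

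**Conclusion.** The point holds in a limited form. The stated reason for automatic withdrawal is wrong for partial revisions, and the participant-level wording conflicts with the hip as the unit of study. The consequence is uncollected data: 2-year OHS for hips revised earlier, later events on retained study components, re-revisions, and possibly the follow-up of an unrevised other hip.

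The effect on the primary mean is modest, about 0.1 to 0.7 points in favour of the device. This rests on an assumed 10 to 20 point shortfall and on revision fractions of 1.3 to 3.3% from the protocol's background cohorts, which used other inserts or mixed implants. The sample size and power are untouched. The more important loss is to the 10-year safety and component-survival aims; the documents do not allow it to be quantified, because they do not say how many revisions will be partial or how many patients bilateral.

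**What to change.** Amend Section 8.4 and reconcile it with Sections 6.0, 6.2, 7.4, 10.1 and 10.2:

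1. Apply the end-of-study marking per hip ID, not per participant, and state that an unrevised other hip continues.
2. At each revision, record which study components remain in situ.
3. Continue OHS, adverse-event and revision data collection for revised hips to 10 years, subject to consent, using the existing visits, home questionnaires and telephone contacts.
4. Report the 2-year OHS both including revised hips and for unrevised hips only, stating which is the main result.

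This changes data collection only, not patient care. The cost is a protocol amendment with ethics approval, a few more questionnaires and calls (roughly 1 to 3 hips per 100 by 2 years at the fractions above), and a mean OHS gain that may look slightly less favourable.

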9.0 DATA MANAGEMENT

9.1 Data Collection and Review

This study will be conducted in compliance with ISO 14155:2020. Data will be collected by the study site(s) in accordance with the approved protocol. All data will be accessible to the study site(s) for use in submissions for research publications, presentations, and to Corin, as Sponsor, for use in submissions to regulatory bodies or other similar authorities.

The study patients will be able to complete the questionnaires on a paper or electronic format. In cases of the participant prefers to complete the questionnaires on paper, the data will be then transferred by the site into the eCRF.

Data will be entered into a secure, web-based, password protected application design to support electronic data capture (EDC). The application to be used for this study is Medrio R41.5. Medrio meets all global data collection regulations - such as ICH GCP, 21 CFR, GDPR, and HIPAA. Only the study investigator(s) or delegated clinical study staff should perform modifications or corrections to eCRF data. Traceability of any modification will be captured via the audit trail to reflect the reason for the change. Medical records and patients' files will be stored electronically and retained by the study site. The study patients will be able to complete the questionnaires on a paper or electronic format. In cases of the participant prefers to complete the questionnaires on paper, the data will be then transferred by the site into the eCRF.

The Investigator should ensure the accuracy, completeness and timeliness of the data reported in the eCRFs and in all required reports. All data reported should be consistent with the source documents.

The Investigator is responsible for preserving data and documentation related to the study during the study and at the end, until Sponsor's communication. Upon request of the Sponsor or regulatory authorities, the Investigator should make available for direct access all requested study-related records.

